# 1. General Information

## 1.1. STUDY TITLE

Bile Reflux Post Bariatric Surgery: A Cohort Study

## 1.2. TRIAL REGISTRATION NUMBERS

WHO Universal Trial Number: U1111-1213-1261

Australian New Zealand Clinical Trials Registry (ANZCTR): ACTRN12618000806268

- Available at: <http://www.ANZCTR.org.au/ACTRN12618000806268.aspx>

## 2. Study Objectives

### 2.1. PURPOSE OF STUDY

#### 2.2. PRIMARY OBJECTIVE

- To evaluate whether laparoscopic single anastomosis gastric bypass (LSAGB), laparoscopic Roux-en-Y gastric bypass (LRYGB) and laparoscopic sleeve gastrectomy (LSG) operations result in increased bile reflux, as determined by the presence of bile acids in the stomach and oesophagus, with or without stomach/oesophageal tissue damage

#### 2.3. SECONDARY OBJECTIVES

- To determine the impact of cholecystectomy on the rates and severity of bile reflux after weight-loss surgery
- To further evaluate the safety and efficacy of LSAGB, LSG and LRYGB
- To evaluate the patient tolerability of hepatobiliary scintigraphy, oesophageal reflux testing and endoscopy

#### 2.4. RESEARCH QUESTIONS

- Do LSAGB, LRYGB and LSG increase the incidence or amount of bile refluxing into the stomach and oesophagus?
- What is the patient tolerability of hepatobiliary scintigraphy and oesophageal impedance testing?

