##### **4.5.2. PRE-SURGICAL WORK UP**

- Participants will undergo the following investigations pre-operatively:
  - Endoscopy, including:
    - Gastric (+/- oesophageal) biopsies
    - Gastric aspirates for biochemical analysis
  - Blood testing

- Complete blood examination
- Serum levels of glucose and HbA1c
- Quantification of fasting lipids
- Weight and height will be measured for body mass index
  - Hip and waist circumference will also be measured to evaluate central obesity index

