#### 4.5.5. FOLLOW-UP

- Participants will be contacted 4-6 weeks post-operatively to assess recovery and confirm continued participation in the study
- Participants invited at 6 months post-operatively to complete the same GerdQ Questionnaire (Appendix 4), in addition to a 'Investigations Tolerability Questionnaire' (Appendix 5)
- Participants who **have not had previous gallbladder surgery** will be invited to undergo the following investigations at 6 months post-operatively:
  - HIDA scan
    - To be performed at the Royal Adelaide Hospital in the Nuclear Medicine Department
    - Biliary scanning will be performed in all subjects following a 6-hour period of fasting and 24-hour abstinence from opiate containing medicine
    - Patients will be injected intravenously with 180 MBq 99mTc DIDA and then dynamic scans will be performed for 100 minutes on a GE, discovery D670 gamma camera using a LFOV with the patient lying supine on the scanning bed
    - A lipid-rich 'fatty meal' (60mL of *Calogen*) will be ingested orally after 30 minutes to stimulate gallbladder emptying

- Following this a SPECT CT scan will be performed of the abdomen for more accurate anatomical localization of activity
    - Delayed imaging may be performed depending on biliary function but only a single low-dose CT will be performed.
  - Endoscopy
    - Gastric (+/- oesophageal) biopsies
    - Gastric aspirates for biochemical analysis
  - Blood testing
    - Complete blood examination
    - Serum levels of glucose and HbA1c
    - Quantification of fasting lipids
  - Weight and height will be measured for body mass index
    - Hip and waist circumference will also be measured to evaluate central obesity index
- Participants who **have undergone previous gallbladder surgery** will only undergo the HIDA scan and symptom questionnaire.
- At 6 months after surgery, if a patient experiences clinically troublesome symptoms and a deterioration in symptom score is noted, then the patient will be offered oesophageal manometry and pH-impedance testing to evaluate swallowing function and to assess the presence of reflux in the oesophagus.

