## 7.2. PRE-OPERATIVE WORKUP

The current standard pre-operative work-up for patients at the Royal Adelaide and Queen Elizabeth Hospitals is for biometric measurements (height, weight and BMI), endoscopy, routine blood testing and selective use of oesophageal manometry and 24-hour pH-impedance reflux testing. All cohorts in the study will undergo these standard investigations, with selective use of manometry and pH-impedance testing as described earlier.

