## 7.3. POST-OPERATIVE FOLLOW-UP

Post-operative follow-up investigations will be performed at 6-months post-operatively. This time frame will provide sufficient time for patients to recover from their operation and returned to their usual activities.

Standard follow-up investigations after bariatric surgery at the Royal Adelaide and Queen Elizabeth Hospitals are biometric measurements (height, weight and BMI), routine blood testing and assessment of symptoms.

In addition to the above standard follow-up, all participants of this study will undergo hepatobiliary scintigraphy to evaluate bile reflux. This investigation has been used previously to assess for reflux (see section 3 of this protocol) and has more recently been used to evaluate reflux after weight loss surgery (24). For the specific safety considerations regarding radiation exposure with hepatobiliary scintigraphy, see section 8 of this protocol.

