## Statistical Analysis of data

- Statistical analysis will be undertaken for the primary outcomes relating to the three types of bariatric surgery being utilised in current clinical practice using commercially available statistical programs in consultation with professional statistical advice from our Unit's established connection with a health research statistician.
  - Normally distributed data will be reported as mean  $\pm$  standard error of the mean and statistical comparisons between groups will be made using parametric statistical tests.
  - Data that is not normally distributed, will be analysed using non-parametric statistics with reporting of median (interquartile range) and comparisons by applying non-parametric statistical tests with post-hoc analysis for differences across the 3 surgical groups.
  - Proportionate data will be compared using tests such as a Fisher's exact test or  $X^2$  test.
- The results will be presented at a relevant scientific forum and subsequently be submitted for publication in a peer-reviewed medical journal.

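### The primary question asks whether each operation increases bile reflux, but HIDA is scheduled only after surgery and the stated comparison is between operations, so the plan as written does not answer it

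*Protocol*

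**What the plan says.** Section 2.2 sets the primary objective as whether the three "operations result in increased bile reflux, as determined by the presence of bile acids in the stomach and oesophagus". Section 2.4 repeats it as a question: "Do LSAGB, LRYGB and LSG increase the incidence or amount of bile refluxing into the stomach and oesophagus". Both ask about a change.

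Assessments:

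- **Before surgery.** Section 4.5.2 opens its list with "Participants will undergo the following investigations pre-operatively" and names endoscopy with gastric (and possibly oesophageal) biopsies, "Gastric aspirates for biochemical analysis", blood tests and body measurements. Section 7.2 describes standard work-up, beyond body measurements, as "endoscopy, routine blood testing and selective use of oesophageal manometry and 24-hour pH-impedance reflux testing". Neither list includes HIDA.
- **At 6 months.** Section 4.5.5 says that participants without previous gallbladder surgery "will be invited to undergo the following investigations at 6 months post-operatively": HIDA, then the same endoscopic samples, bloods and measurements. Section 7.3 places HIDA in post-operative follow-up: "In addition to the above standard follow-up, all participants of this study will undergo hepatobiliary scintigraphy to evaluate bile reflux".

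Section 5.1 lists HIDA first among the primary outcomes, followed by impedance, bile acids in aspirates, and histology. Section 4.4 sizes the study for a difference between the best and worst operation (5% v 50%). For normally distributed data, section 9 says "statistical comparisons between groups will be made using parametric statistical tests". Non-normal data are compared across the three surgical groups, and the tests named for proportions are Fisher's exact and chi-squared. Under section 4.5.3 the surgeon and patient choose the operation.

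**The concern.** The objective concerns change within patients having a given operation. The stated comparison concerns differences between operations after surgery. These are separate questions, and the answer to one does not give the other.

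- **No difference between operations** is compatible with all three raising reflux equally, or with none raising it.
- **A difference between operations** is compatible with no operation raising reflux, if patients who already refluxed tended to receive one operation. Allocation is not randomised, and section 7.1 says that individual patient factors drive the choice.
- **A positive scan at 6 months** may have been positive before surgery. Section 3 itself describes obesity as an independent risk factor for gastro-oesophageal reflux, so a clean baseline cannot be assumed.

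Section 3.5 hopes to give clinicians clear evidence on the safety of LSAGB. A null between-operation result could be read as showing no increase when it shows nothing of the kind.

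**Working it through.** **1. What the stated sample size answers.** Inputs from section 4.4: 5% v 50%, power 80%, alpha 0.05 (two-sided assumed), Fisher's exact test, inflation factor 1.2, 10% loss, three arms.

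- Exact Fisher power by enumeration: 16 per arm gives 77.7%, 17 gives 81.3%. So 17 per arm.
- Clustering: 17 × 1.2 = 20.4, rounded up to 21.
- Loss: 21 × 1.1 = 23.1, rounded up to 24.
- Total: 24 × 3 = 72.

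The stated 72 reproduces, as the number for comparing post-operative rates between two operations.

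**2. Which measures have a before value (main cohort).**

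| Measure | Before surgery | 6 months |
|---|---|---|
| HIDA | not scheduled | yes |
| Gastric aspirate | yes | yes |
| Gastric biopsy | yes | yes |
| Oesophageal biopsy | optional | optional |
| Oesophageal aspirate | not scheduled | not scheduled |
| pH-impedance | selective | offered only if symptoms are troublesome and worse |

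Planned HIDA baselines: 0 of 72. Gastric pairs per operation: 24 × 0.9 = 21.6, so about 21.

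**3. What the between-operation test does when the answer is yes.** Suppose every operation raises reflux from 5% to 50%. The pre-operative rate is an assumption, since the protocol gives none. At 6 months each pair of operations is then 50% v 50%. Exact two-sided Fisher with 21 per arm rejects in 2.0% of trials, which is simply the size of the test.

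**4. What it does when the answer is no.** As a deliberately extreme case, suppose one operation's patients reflux at 50% before and after, and another's at 5% before and after. Fisher with 21 per arm has 91.1% power at 5% v 50%, so it would usually declare a difference although no operation changed anything.

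**5. What a paired test could do.** Exact two-sided McNemar, alpha 0.05, 21 pairs. Let p01 be the probability of gaining reflux and p10 of losing it. The lower figure takes before and after as independent: p01 = (1 − pre) × post, p10 = pre × (1 − post). The upper figure assumes that nobody loses reflux: p01 = post − pre, p10 = 0. For 5% to 50% these are 0.475 and 0.025, or 0.45 and 0.

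| Assumed change | Power |
|---|---|
| 5% to 50% | 88-96% |
| 10% to 50% | 72-90% |
| 20% to 50% | 39-64% |
| 30% to 50% | 16-23% |

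These figures make no allowance for surgeon clustering or for testing three operations.

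**6. Smallest significant paired result.** With all d discordant pairs in one direction, P = 2 × (1/2)^d: d = 5 gives 0.063, d = 6 gives 0.031, d = 7 gives 0.016. Six suffice at 0.05. At 0.05/3 = 0.0167, seven are needed. Both are best cases, since any pair in the other direction raises P.

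**The case against.** The strongest reply is that the objective does not name HIDA. Section 2.2 defines increased reflux by the presence of bile acids, and section 9 says that gastric aspirates and biopsies are examined for bile acids. Both are taken before surgery and at 6 months, so the measure closest to the objective does have a baseline in the stomach. This stands. A reader might infer that the primary question cannot be answered from this study at all; the documents do not support that.

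Second, section 9 is short and open. It speaks of tests such as Fisher's or chi-squared and of statistical advice, and it excludes no pre/post comparison. Choosing a paired test is commonly left to an SAP. This stands in part: a missing test name alone would be no finding. But the protocol does state its comparison, in both section 4.4 and section 9, and it is a different one from the objective. An SAP could add paired tests on gastric samples; it could not create a HIDA baseline.

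Third, the design is coherent as a comparison between operations, and its sample size reproduces on that basis. True. The mismatch lies between that design and the wording of sections 2.2 and 2.4, and a reader should not infer an error in the figure of 72.

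Fourth, paired gastric data are no full remedy. Oesophageal pairs are sparse, the post-operative sample comes from an altered stomach or pouch, and power is poor if reflux is common beforehand. All of this stands and limits what the fix can deliver.

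**Conclusion.** The point holds as a mismatch between the primary question and the stated comparison. HIDA, as scheduled, supports only a comparison of 6-month reflux between operations. It cannot show that any operation increased reflux, and with allocation by choice even a clear difference may reflect baseline differences. Following sections 4.4 and 9 as written leaves sections 2.2 and 2.4 unanswered.

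The size of the problem is shown by the equal-rise case: 2.0% rejection for the stated comparison against 88-96% power for a paired one. That contrast rests on an assumed 5% pre-operative rate, 21 complete pairs, two-sided alpha 0.05, and no allowance for clustering or multiplicity. At an assumed 30% before surgery, paired power is only 16-23%. It would therefore be too strong to say that the existing samples guarantee an adequate test: they make the increase estimable in the stomach, with precision that depends on an unknown baseline. Because there is no unoperated control, a before-after change also takes in weight loss and anything else that altered over the six months.

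**What to change.** 1. In sections 2.2, 2.4 and 5.1, state that HIDA supports only a between-operation comparison of bile reflux at 6 months, and that the question of increase is addressed by the paired gastric samples.
2. In section 9, add a within-operation paired analysis for the main cohort:
   - presence of bile acids: exact McNemar test, with the paired difference in proportions and its 95% CI;
   - bile-acid concentration and the biopsy markers already listed in section 9: signed-rank test, or mean change with 95% CI;
   - between operations: comparison of change adjusted for the baseline value, noting that this does not remove all confounding by choice of operation.
3. Specify a multiplicity allowance for the three within-operation tests (for example 0.05/3), and let estimates with CIs lead the report.
4. State the limits: the paired data address the stomach and not reliably the oesophagus; concentrations before surgery and in the post-operative pouch may not be fully comparable; the gallbladder sub-group has no endoscopy and so contributes no pairs.

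The cost is some rewording, a few extra analyses and a narrower conclusion from HIDA. No procedure or patient is added.

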# 3. Rationale and Background

An increasing number of patients are receiving operations for morbid obesity. Obesity is an independent risk factor for development of gastroesophageal reflux and weight-loss can significantly improve symptoms. Some weight-loss operations, however, can promote reflux due to the anatomical alterations, and reflux can persist despite weight loss (1). Duodenal contents - bile, bicarbonate and pancreatic enzymes - may reflux back into the stomach and oesophagus, termed *duodenogastroesophageal reflux (DGOR)* or *bile reflux*. It has been well-documented that bile acids, in conjunction with gastric acid, contribute to the development of reflux-type symptoms (heartburn, regurgitation, waterbrash, etc.), erosive oesophagitis and also to the development of Barrett's oesophagus (2, 3).

## 3.1. Bile acids cause oesophageal adenocarcinoma

Bile acids form a group of amphipathic molecules synthesized in pericentral hepatocytes of hepatic acini during carbohydrate metabolism. They are steroid acids, comprising of one cyclopentane and 3 cyclohexane rings, a carboxylic side chain and varying numbers of hydroxyl groups. Under physiologic conditions, essentially all bile acids secreted into bile are conjugated (>98%) with either taurine or glycine, which lowers the acidity index and in turn increases solubility and ionization capability of bile acids. The physiological consequence of conjugation is decreased passive diffusion across cell membranes, thereby maintaining high intraluminal concentrations to facilitate their primary function of lipid digestion and absorption.

Bile acids are most injurious to oesophageal epithelial cells when they are un-ionised, hydrophobic and soluble, resulting in maximal diffusion capability across cell membranes. pKa is a key factor in bile salt solubility. Unconjugated bile acids have a pKa of around 5.1, whereas taurine and glycine conjugated acids have values of approximately pKa 4 and pKa 2 respectively. It follows that in neutral and alkaline solutions, bile acids exist predominantly in their non-injurious ionized form. Furthermore, when bile is acidified to below pH 2, irreversible precipitation of bile acids occurs, decreasing the total number of bile acids found in bile (4). Thus, in solutions with pH 2-6, typical gastric acidity level, bile acids are most injurious with a significant proportion unionized in solution. Human and animal studies support this biochemical data, showing that bile acid-mediated oesophageal damage is potentiated in an acidic compared with weakly acidic and neutral environments (5-7). The majority of duodenogastroesophageal reflux events are known to be acidic rather than neutral or alkaline, increasing the risk of oesophageal damage (8).

Increased oesophageal epithelial permeability is a key feature of reflux-induced tissue damage in the oesophagus. Studies of animal and human oesophageal tissue, both native and cultured, show that epithelial permeability is increased by exposure to bile acids in acidic solutions, and to a lesser degree in weakly acidic and neutral solutions (5-7). Kiroff et al. evaluated this *in vivo*, in anaesthetised rabbits by measuring the rate of H+ disappearance during intra-oesophageal perfusions of varying concentrations of sodium taurocholate in normal saline or 10mmol/L H+ (5). Farre et al. studied rabbit oesophageal tissue *in vitro*, also following exposure to bile acids at varying concentrations and pH, and measuring transepithelial permeability by electron microscopy (6). Results were consistent in both experiments, demonstrating significantly increased H+ disappearance and transepithelial permeability respectively in acidic bile acid solutions, but not in neutral bile acid solutions. Human studies have drawn similar conclusions (7, 9).

Increased epithelial permeability combined with optimal refluxate pH for diffusion of soluble, un-ionised bile acids results in increased translocation of bile acids into epithelial cells. Once intracellular, bile acids are known to incite an inflammatory response and lead to the production of reactive oxygen species, causing oxidative DNA damage and cell death (10). Through these mechanisms, tissue may progressively undergo metaplastic change. This can lead to Barrett's oesophagus and less often, oesophageal adenocarcinoma.

### **3.2. Bariatric surgery can cause bile reflux**

The obesity epidemic is escalating - In 2014, more than 1.9 billion adults aged 18 and above (39% of global population) were overweight with 600 million being obese (11). Medical treatment of obesity continues to yield disappointing results. Obesity surgery consistently results in effective and sustained weight loss with improved quality of life, and remission of obesity-related comorbidities (12). Obesity is an independent risk factor for development of gastroesophageal reflux and weight-loss can significantly improve symptoms. Some weight-loss operations, however, can promote reflux due to the anatomical alterations, and reflux can persist despite the weight loss (1).

Recent advances in obesity surgery include the introduction of new surgical techniques. Currently, the laparoscopic Roux-en-Y gastric bypass (LRYGP) is the 'gold standard' and most commonly performed surgical procedure for weight loss worldwide, however it remains a technically challenging laparoscopic operation with significant associated risk. It is the gold standard as it facilitates sustained weight loss with relatively few adverse outcomes. Laparoscopic sleeve gastrectomy (LSG) is an alternative operative technique increasingly being used for weight loss, however it is associated with an increase in prevalence of gastro-oesophageal reflux. This was shown in a study of 66 obese patients evaluated 1 year after LSG and demonstrated a significant increase in endoscopy-proven gastro-oesophageal reflux and erosive oesophagitis (13).

The third alternative operative technique is the laparoscopic single anastomosis gastric bypass (LSAGB), also known as the 'mini gastric bypass' or the 'omega loop gastric bypass'. This technique is growing in popularity since being first described in 2001 (14). As described by proponents of the technique, there are many advantages: it is quicker to learn; has a shorter operative time (and thus shorter anaesthetic); reduces risk of complications (one anastomosis rather than two) and weight loss as well as glucose tolerance outcomes are comparable to LRYGP (15, 16). Despite these results, LSAGB is not being as rapidly adopted by bariatric surgeons as might be expected. The low uptake relates to controversy concerning the theoretical long-term harm and potentially carcinogenic effects of bile reflux into the gastric remnant and the oesophagus after LSAGB (17).

The effect of gallbladder removal on the incidence of bile reflux remains debatable. Increased rates and severity of bile reflux post-cholecystectomy has been reported by some studies(18, 19), and refuted by others (20). In patients undergoing weight-loss surgery, an operation that may exacerbate bile reflux, the additive impact of cholecystectomy on bile reflux remains unknown. Given the significant end-sequelae, namely carcinogenesis, the effect of cholecystectomy on bile reflux needs to be examined to guide surgical decision making.

### **3.3. Investigative techniques for diagnosis of bile reflux**

The intermittent nature of DGER is one of the challenges for the development of an optimal diagnostic investigation. The available techniques include HIDA scintigraphy, endoscopy and biopsies, 'Bilitec' spectrophotometer probe and oesophageal impedance-pH testing. Of these techniques, HIDA scintigraphy is the least invasive but only provides a short window (1-2 hours) for the capture of DGER events. A more complete DGER profile requires prolonged monitoring, but none of the current ambulatory techniques are ideal. Ambulatory Bilitec monitoring was specifically developed for the detection of bile reflux, but is prone to errors, particularly false positive readings, whereas pH testing (acid reflux) and also combined impedance-pH monitoring (acid and non-acid reflux) do not directly detect bile reflux.

HIDA scintigraphy, a radio-nuclide scan, has superior patient tolerability over catheter-based methods, with a shorter monitoring time (1-2 hours compared with 24 hours) and a non-invasive nature. Published figures for sensitivity and specificity for each technique are lacking, limiting direct comparison of techniques. Of available studies, HIDA scintigraphy shows superior sensitivity over EGD and aspiration for diagnosis of DGER (21). However, for quantification of refluxate composition or for when visualization of the oesophagus is required to determine any mucosal damage then endoscopy with fluid aspiration and tissue biopsy would be most appropriate.

